#### 4.2.6 Summary and Representation of Data

Continuous data will be summarized in terms of mean, standard deviation (SD), median, minimum, maximum, and number of observations, unless otherwise stated.

Categorical data will be summarized in terms of the number of participants providing data at the relevant time point (n), frequency counts, and percentages.

The minimum and maximum will be reported to the same number of decimal places as the raw data recorded in the database. The mean and median will be reported to one more decimal place than the raw data recorded in the database. The SD will be reported to two more decimal places than the raw data recorded in the database. In general, the maximum number of decimal places reported shall be four for any summary statistics.

Percentages between 1% and 99%, inclusive, will be rounded to integers. Percentages greater than 0%, but less than 1%, will be reported as <1%, and percentages greater than 99%, but less than 100%, will be reported as >99%. If for any summary table, n is less than three then only n, minimum, and maximum should be presented, and other summary statistics will be left blank.

#### 4.3 Software

All report outputs will be produced using SAS® version 9.3 or later in a secure and validated environment.

The PK analyses will be conducted using Phoenix® WinNonlin (WNL) version 8.3 or later in a secure and validated environment.

All report outputs will be provided to the Sponsor in RTF for individual TLFs and PDF for combined TLFs format.

#### 4.4 Study Participants

##### 4.4.1 Analysis Sets

Analysis Set	Definition / Criteria	Analyses Evaluated
Screened	
 
• All participants who were screened for eligibility
 
	
 
• Study Population
 

Enrolled	
 
• All participants who entered the study (who successfully passed screening)
 
• Note screening failures (who never passed screening even if rescreened) and participants screened but never enrolled into the study (Met eligibility but not needed) are excluded from the Enrolled analysis set as they did not enter the study.
 
	
 
• Study Population
 

Safety/Exposed	
 
• All participants who received at least one dose of study intervention.
 
	
 
• Safety
 

Analysis Set	Definition / Criteria	Analyses Evaluated
	
 
• Data will be reported according to the actual study intervention.
 
	
PK	
 
• All participants in the Safety analysis set who had at least 1 non-missing PK assessment (non-quantifiable values will be considered as non-missing values).
 
• Data will be reported according to the actual study intervention.
 
• Used for some displays required by EudraCT. Studies with single arm should use the text “Assigned rather than Randomized”.
 
	
 
• Primary analysis
 

PD	
 
• All participants in the Safety analysis set who had at least 1 non-missing ECG assessment.
 
• Data will be reported according to the actual study intervention.
 
	
 
• Primary analysis
 

#### 4.4.2 Disposition of Participants

A clear accounting of the disposition of all participants who enter the study will be provided, from screening to study completion.

A summary of participant study/treatment completion status and reason for study withdrawal will be provided for the enrolled set. This display will show the number and percentage of participants who withdrew from the study, who have completed the study or have discontinued study treatment including primary reasons for study withdrawal and discontinuation of study treatment.

A by participant listing of study discontinuation will be presented for the enrolled set. The listing will include last dose date and reasons for study treatment discontinuation.

A by participant listing for screen failure will be provided including reason for screen failure for all participants.

#### 4.4.3 Protocol Deviations

All protocol deviations are predefined in the separate document, Protocol Deviation Assessment Plan.

##### 4.4.3.1 Protocol Deviations with Non-PK Implications

The defined protocol deviations will be collected during the study period by site monitor/clinical team and programming team. All deviations will be described when relating to:

- Study inclusion or exclusion criteria
- Conduct of the study
- Participant management or participant assessment
- Handling of the participant's rights.

##### 4.4.3.2 Protocol Deviations with PK Implications

Protocol deviations that may potentially impact PK parameter derivations include, but are not limited

to:

- Emetic episode within 1 hour after administering study drug
- Missed PK samples that impact estimation of PK parameter(s)
- Concomitant medications not authorized by protocol.
- PK samples obtained out of allowance window that may impact the estimation of PK parameter(s)
- Food intake deviations (not completely consumed or consumed outside of time allowed)

Protocol deviations (mentioned in Sections [4.4.3.1](#) and [4.4.3.2](#)) and analysis sets will be reviewed in the (blinded) data review report meeting to decide inclusion or exclusion of participant(s) from analyses sets. Decisions regarding the exclusion of participants and/or participant data from analyses will be made prior to database lock and will be documented and approved.

A by-participant listing of important and non-important protocol deviations will be provided including participant identifier; exclusion from specific analysis sets; and protocol deviation classification, and protocol deviation description and exclusion from specific analysis sets.

#### 4.5 Demographics and Baseline Characteristics

The demographic characteristics (e.g., age, race, ethnicity, sex, height, body weight, body mass index [BMI]) will be summarized and listed by participant for the Safety Set and enrolled set.

Age, height, weight and BMI will be summarized using the mean, SD, minimum, median, and maximum. The count and percentage will be computed for sex, race, and ethnicity. The summary table will be displayed by treatment for the Safety Set.

#### 4.6 Medical History

Medical and surgical history will be coded using Medical Dictionary for Regulatory Activities (MedDRA®), Version 26.0 or higher and assigned to a System Organ Class (SOC) and Preferred Term (PT). Summary of Medical history will be provided by SOC and PT for Safety Analysis Set.

#### 4.7 Prior and Concomitant Medications

##### Prior and Concomitant Medication:

Prior medications are those that started and stopped before the first dose of IMP. Concomitant medications are those taken after first dosing (including medications that started before dosing and continued after).

Prior and concomitant medication will be coded according to the World Health Organization Drug Dictionary (WHO-DD) (Version March 1, 2023 or latest) and will be classified by Anatomical Therapeutic Chemical (ATC) categories.

By participant listings of prior and concomitant medications will be provided for the Safety Set and will include the following information: reported name, preferred term (PT), the route of administration, dose, frequency, start date/time, duration, and indication.

#### 4.8 Treatment Exposure and Compliance

##### 4.8.1 Treatment Exposure

Summary of treatment exposure will be provided in terms of number of dose administered based on Safety population for the IP administration. A by-participant listing of participant exposure to study

drug will be generated. The listing will include dose, date and time, unit, formulation, route, and frequency.

#### 4.8.2 Compliance

Dose compliance at site and dosing compliance while dosing at home will be evaluated. Participants will take the planned dose under direct supervision while on site, and via video-call while dosing at home.

- Compliance (%) at site will be calculated as  $100\% * \text{total number of actual taken site doses} / \text{total number of planned site doses}$ .
- Compliance (%) at home will be calculated as  $100\% * \text{total number of actual taken home doses} / \text{total number of planned home doses}$ .

#### 4.9 Analysis Supporting Primary Objective(s)

##### 4.9.1 Primary Endpoint(s)

The primary endpoint is the change from baseline in QTc ( $\Delta\text{QTc}$ ), where baseline is the pre-dose collection obtained on visit 2 (Day -1, 0.25h before the planned dosing time of Day 1).

QTc for primary analysis will be measured at Visits 2 (Day -1), 3 (Day 7), 4 (Day 14) and 5 (Day 21) as outlined in the SoA. At each time point where replicate ECG is obtained, then mean of the triplicates will be used for deriving baseline and change from baseline.

##### 4.9.2 Statistical Hypothesis, Model, and Method of Analysis

A random-coefficient linear mixed-effects model will be fit to all available paroxetine concentration -  $\Delta\text{QTc}$  data pairs, as described in a white paper (Garnet C et al., 2018 [3]). In this model,  $\Delta\text{QTc}$  is the dependent variable and paroxetine concentration and time after dose and baseline are independent variables, it takes the form of:

$$\Delta\text{QTc}_{i,k} = (\theta_0 + \eta_{0,i}) + (\theta_1 + \eta_{1,i}) * C_{i,k} + \theta_{2,k} * \text{TIME}_{i,k} + \theta_3(Q\text{Tc}_{i,k=0} - \overline{Q\text{Tc}_0}) + \varepsilon_{i,k}$$

In this equation:

- $\Delta\text{QTc}_{i,k}$  is the change from baseline in QTc for participant  $i$  at time  $k$ ;
- $\theta_0$  is the population mean intercept in the absence of a treatment effect;
- $\eta_{0,i}$  is the random effect associated with the intercept term  $\theta_0$ ;
- $\theta_1$  is the population mean slope of the assumed linear association between concentration and  $\Delta\text{QTc}_{i,k}$ ;
- $\eta_{1,i}$  is the random effect associated with the slope  $\theta_1$ ;
- $C_{i,k}$  is the concentration for participant  $i$  and time  $k$ ;
- $\theta_{2,k}$  is the fixed multilevel categorical effect associated with time factor. If inspection of the Day -1 data suggests a time-dependent trend, alternative parameterization for the time variable, for example based on (co)sine function such as described in Koch et al 2002, could be used if relevant;
- $\theta_3$  is the fixed effect associated with the difference of each baseline values to the overall mean (Baseline  $\text{QTc}_{i,k=0}$ ,  $\text{QTc}_0$  is overall mean of  $\text{QTc}_{i,k=0}$ , i.e., the mean of all the baseline (= time 0) QTc values).

It is assumed the random effects ( $\eta_{0,i}$  and  $\eta_{1,i}$ ) are normally distributed with mean [0,0] and an unstructured covariance matrix G, whereas the residuals are normally distributed with mean 0 and variance R. In case of the unstructured covariance matrix for random effects is not supported by the data or results in null estimates, and may result in non-convergence problems, other simplified or reduced structures will be investigated (Variance component with 2 random effects, 1 for slope and 1 for intercept, variance component with 1 random effect for intercept or slope).

The  $\Delta QTc$  and paroxetine concentrations corresponding to all doses (20, 40, and 60mg) will be used for the modelling (Both drawn from each participant at same time intervals). Moreover,  $\Delta QTc$  obtained on Visit 2 (Day -1) after baseline will be included in the model with paroxetine concentrations set to 0. This model assumes a linear correlation between paroxetine plasma concentration and  $\Delta QTc$ . While it is assumed that such a correlation (if at all) can be considered linear at clinically meaningful doses, other parameterizations such as the classical Emax function may be explored if the linear approach is found inappropriate.

The model parameters will be estimated including the precision around the parameter estimates using a maximum likelihood approach.

The following SAS® code will be used for the random-coefficient linear mixed-effects model:

```
PROC MIXED DATA=ADEG (WHERE=(XXXX)) NOITPRINT CL NOCLPRINT METHOD=ML PLOTS=NONE;
ODS OUTPUT SOLUTIONF=SOLF ESTIMATES=ESTF COVPARMS=COV;
CLASS USUBJID ATPTN ;
MODEL CHG=BASEC ATPTN PCSTRESN / DDFM=KR SOLUTION ALPHAP=.05 CL RESIDUAL
OUTPM=PRED OUTP=IPRED;
RANDOM INT PCSTRESN /SUB=USUBJID TYPE=UN;
ESTIMATE "DDQTC_60MG" INT 1 PCSTRESN CMAX60MG /CL ALPHA=.1;
RUN;
```

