**Categorical description of time effect on  $\Delta$ QTcF**

The standard model contains a categorical variable to account for time dependent changes in QTc ( $\theta_{2,k} * TIME_{i,k}$ ). This parameterization is agnostic to any trends in such changes, and may be better represented by other functions. In particular, it has been reported in literature that (co)sinusoidal functions may describe the change in QTc due to diurnal / circadian variation, e.g. Koch & Raschka 2002 [5]. Inspection of the Day -1 serial QTc data may help to elucidate such trends in change of QTc over time and drive the specification of such a time-dependent function.

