#### 4.9.2.3 Summary of measure

Individual Cmax values for participants at the 60 mg dose will be used to calculate the Cmax geometric mean. Based on the estimated model, the calculated geometric mean Cmax for dose 60 mg will be used in the fitted model to predict the upper limit of the 90% CI of  $\Delta QTc$  at dose 60 mg as follows (in the case of a linear model):

$$\overline{\Delta QTc_{60mg}} = \theta_0 + \theta_1 Cmax(60mg)$$

$$90\% CI = \overline{\Delta QTc_{60mg}} \pm t(0.95, DF) \times SE$$

$$SE = \sqrt{var(\theta_0) + C_{max}^2(60 mg) var(\theta_1) + 2C_{max}(60 mg) \times cov(\theta_0, \theta_1)}$$

Where:

- $\overline{\Delta QTc_{60mg}}$  is the predicted  $\Delta QTc$  at 60 mg;
- $\theta_0$  is the estimated fixed intercept term;
- $\theta_1$  is the estimated fixed slope for concentrations;
- $t(0.95, DF)$  is the 95th quantile from the student distribution with  $DF$  degrees of freedom;
- SE is the standard error ;
- $var(\theta_0)$ ,  $var(\theta_1)$  and  $cov(\theta_0, \theta_1)$  are respectively the variance of  $\theta_0$  and  $\theta_1$  and their covariance.

The summary measure of the study is the geometric mean and 90% CI of the predicted  $\Delta QTc$  at 60 mg Cmax. If the upper bound of 90% CI for this predicted  $\Delta QTc$  falls below the 10 msec mark, the conclusion of the study is that there is no clinically relevant QTc prolongation up to and including the 60 mg dose. In case the upper 90% CI limit does not fall below the 10 msec mark, the same evaluation will be performed for the  $\Delta QTc$  at the geometric mean Cmax of the 40 mg once daily dose.

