10. Vital signs, laboratory assessments (coagulation parameters, haematology with differential, clinical and liver chemistry, pregnancy test, and paroxetine concentrations samples) and ECG data will all be captured at visits on site. During the treatment period, all laboratory samples and vitals (including one paroxetine concentration sample) should be obtained pre-dose.
11. All ECGs will be performed in triplicate collected within 5 min at each timepoint. ECG triplicates will be performed once at Screening (Visit 1), and at Follow-Up Visit and at discontinuation or withdrawal visits. At Visits 2 (Day -1), 3 (Day 7), 4 (Day 14), and 5 (Day 21) ECG triplicates will be performed 15 min pre-dose (-0.25 h) and post-dose at the following timepoints 1, 2, 3, 4, 4.5, 5, 5.5, 6, 8, 10, 12h. Each ECG triplicate will be combined with paroxetine concentration assessment. Paroxetine concentrations at Visits 3 (Day 7), 4 (Day 14), and 5 (Day 21) will be procured at the following timepoints: -0.25, 1, 2, 3, 4, 4.5, 5, 5.5, 6, 8, 10, 12 h. One sample will be collected for paroxetine concentrations on Day -1 at 0.25h (pre-dose). The paroxetine dose should be taken at the same clock time each time, at a time approximately between 07:00-09:00 (7/10 am). When scheduled for the same time, ECGs should be performed before blood sampling to avoid impact on ECG parameters.
12. .
13. At Visits 2 (Day -1), 3 (Day 7), 4 (Day 14), and 5 (Day 21), follow-up visit and at discontinuation or withdrawal visits, serial ECG review will be performed by Mortara system
14. Negative urine pregnancy test result must be confirmed prior to dosing in female participants of reproductive potential. If a urine test cannot be confirmed as negative (e.g., an ambiguous result), a serum pregnancy test is required. In such cases, the participant must be excluded from participation if the serum pregnancy result is positive.
15. FSH test be performed for postmenopausal women only.
16. COVID-19 testing will be performed as per site practice.
17. Participants will be discharged from the clinic 3 hours after the morning dose on Study Days 1, 8, and 15 (Visit 2, 3, 4) to subsequently take paroxetine doses at home until the next visits in clinic.
18. Participants will get discharge on either Day 21 or Day 22 (may stay overnight) as per the convenience.

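### The SAP lets a (co)sine curve replace the 12-level time factor after a look at Day -1; with a prediction formula that has no time term, this can shift the value compared with 10 msec without any drug effect

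*SAP*

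**What the plan says.** SAP 4.9.2 defines the time term: it "is the fixed multilevel categorical effect associated with time factor". The planned code agrees, with the nominal time variable as a class effect ("CLASS USUBJID ATPTN"). The schedule in SAP 6.1 has concentrations "procured at the following timepoints: -0.25, 1, 2, 3, 4, 4.5, 5, 5.5, 6, 8, 10, 12 h" on Days 7, 14 and 21, with ECGs at the same times on those days and on Day -1. The factor therefore has 12 levels.

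The same bullet opens an alternative: "If inspection of the Day -1 data suggests a time-dependent trend, alternative parameterization for the time variable", with a (co)sine function as the example, "could be used if relevant". SAP 4.9.2.1 returns to this and says of the categorical form: "This parameterization is agnostic to any trends in such changes, and may be better represented by other functions". Inspection of the Day -1 series may then "drive the specification of such a time-dependent function".

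The decision value is set in SAP 4.9.2.3: "the calculated geometric mean Cmax for dose 60 mg will be used in the fitted model". The written prediction is θ0 + θ1 × Cmax, and its standard error contains only the variances and covariance of θ0 and θ1. The ESTIMATE line likewise names only the intercept and the concentration. The study concludes that there is no clinically relevant prolongation if the upper 90% bound of that value is below 10 msec.

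The Day -1 records after baseline enter the same fit with concentration set to zero (SAP 4.9.2). The model in Protocol 9.3.2.2 has a fixed time effect and mentions no alternative time function. SAP 4.17 lists only a change to the Enrolled set, and SAP 4.9.6 plans no supplementary analyses.

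**The concern.** A time trend on Day -1 is the reason for having a time factor. With one level per nominal time, the factor absorbs any pattern common to all participants at those times. Finding a trend is therefore not a reason to replace it with a curve that imposes a shape.

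The swap would be harmless if only the concentration slope mattered, but the decision also uses θ0. Under the factor, θ0 refers to the sampled times (their average or one reference level; the SAP does not say which). Under a (co)sine, θ0 is the mean level of the curve over its full period. The two quantities can differ, and the difference has nothing to do with paroxetine.

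The choice would be made after looking at QTc values that are part of the fitted data. There is no stated criterion, no requirement to report both fits, and a 90% CI that does not reflect the choice. One comparison with 10 msec decides the study, so the two models could lead to opposite conclusions.

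**Working it through.** **Plan's own figure.** For 36 participants without dropout, SAP 4.16 gives probabilities of 0%, 0.6% and 82.5% that the upper limit is at least 10 msec, for true effects of 0, 5 and 10 msec. The 0.6% cell implies SE = 5 / (2.512 + 1.645) = 1.20 msec. With that SE, an unbiased normal estimate gives 95% at 10 msec, not 82.5%. The table cannot be rebuilt because its simulation inputs are not given. That is a separate matter; here it only shows that an SE near 1.2 msec is a reasonable scale.

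**Inputs.**
- From the documents: 36 participants; 11 Day -1 records (12 less the baseline) plus 3 × 12 on-drug records each, so 36 × 47 = 1,692 rows if complete; the 12 nominal times; the prediction formula; the 10 msec limit.
- Assumed, because the documents give none of them: intercept SD 6 msec, residual SD 6 msec, slope SD 0.7 msec per unit concentration, relative Cmax 1 : 2.4 : 4 with a peak at 5 h, and diurnal swings of 2, 5 or 10 msec peak to trough. Variance components were treated as known (generalised least squares); no full maximum-likelihood fit was completed.

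**Step 1: precision.** SE of θ0 + θ1 × Cmax(60 mg):

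| Time term and reading of θ0 | SE (msec) |
|---|---|
| 12-level factor, averaged over the 12 times | 1.159 |
| 24 h cosine, averaged over the same 12 times | 1.159 |
| 24 h cosine, θ0 as curve mean | 1.196 (+3%) |
| Two harmonics, θ0 as curve mean | 1.474 (+27%) |
| 12-level factor, θ0 as the 12 h level | 1.259 |

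The slope SE is 0.1647 with the factor and 0.1646 with the cosine. The only gain is against a single 12 h reference level: 1.196 / 1.259 = 0.95, or 1.645 × 0.063 = 0.10 msec on the bound.

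**Step 2: shift if the true pattern is a 24 h cosine.** Write the pattern as m + A cos(2π(t − φ)/24). The fitted curve returns m as θ0. The 12-level average is m plus A times the mean cosine at the sampled times. Over those times the mean of cos(2πt/24) is 0.204 and the mean of sin(2πt/24) is 0.626, so the largest difference is A × √(0.204² + 0.626²) = 0.658 A. With A as half the swing:
- swing 2 msec: 0.658 × 1 = 0.7 msec
- swing 5 msec: 0.658 × 2.5 = 1.6 msec
- swing 10 msec: 0.658 × 5 = 3.3 msec

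The sign depends on phase. Against a single 12 h reference level the maximum is A itself: 1.0, 2.5 or 5.0 msec.

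**Step 3: shift if the shape is wrong.** A true 12 h wave fitted with a 24 h cosine moves the value by up to 1.2, 3.1 or 6.2 msec against the 12-level average, for the same three swings. The θ1 × Cmax part moves by at most 0.4 msec in any scenario, so nearly all of the shift lies in θ0.

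**Step 4: same prediction times.** If the cosine is fitted but its prediction is averaged over the 12 sampled times, the value moves by at most 0.24 msec in every scenario tried, and not at all when the cosine is the true shape.

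**Step 5: effect on the decision.** Take a time-averaged value of 7 msec. The chance that the bound falls below 10 is Φ(3/1.159 − 1.645) = Φ(0.94), about 82% (82% in simulation). After a swap with a 5 msec swing and the worst phases:
- shift −1.645: Φ(4.645/1.196 − 1.645) = Φ(2.24) = 99%
- shift +1.645: Φ(1.355/1.196 − 1.645) = Φ(−0.51) = 30%

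With a 10 msec swing the two figures are 100% and 3%.

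**The case against.** The strongest reply is that the shift comes from how θ0 is read and not from the curve. Step 4 bears this out. The SAP gives its formula for the linear case and does not say that a cosine model would be read at its mean level. So the harm needs the swap and the θ0-only formula together, and deleting the (co)sine option alone would leave the prediction time unstated.

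A reader might infer that a (co)sine can only fit worse. The documents do not support that in general. It holds for a curve in nominal time after dose, but SAP 4.9.2.1 speaks of diurnal variation, and a clock-time curve is not nested in 12 post-dose levels. The documents give dosing windows of 07:00 to 10:00 (Protocol Table 2, note 11) and 08:00 to 09:00 (Protocol Table 3, note 2). For an assumed 24 h clock-time cosine of amplitude 5 msec, the factor leaves misfit with an SD of about 0.7 msec after the random intercept under the wider window, and about 0.25 msec under the narrower one. That is small, but it is a real limit of the factor.

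A reader might also infer that the decision value will move by several msec. That needs a large swing or a wrong shape, an unfavourable phase and an assumed period. The SAP states no period, and the title of its cited source refers to ultradian variation. Nor is it strictly true that the swap never gains precision (Step 1, last row).

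Two safeguards exist. The trigger uses drug-free data only, which protects the slope but not θ0. SAP 4.9.2.2 requires residual plots against time, which may reveal a poor curve but do not say what happens next. The factor also remains the stated default, with code.

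**Conclusion.** The concern holds in a conditional form. The SAP permits an unspecified replacement of the time factor in the primary model, on a trigger that does not justify it and for no meaningful gain in precision. Because the decision formula has no time term, the swap changes what θ0 stands for.

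The possible shift is up to about 0.7, 1.6 or 3.3 msec for swings of 2, 5 or 10 msec, and up to about twice that under a wrong shape, in either direction. These are worst-phase values. They rest on an assumed 24 h period and assumed swings, and on θ0 being used as SAP 4.9.2.3 writes it. Averaging the prediction over the 12 sampled times reduces the shift to about 0.2 msec at most. The documents do not show that a shift of several msec will occur, or that the option was added to favour a result.

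**What to change.** In SAP 4.9.2 (the time-effect bullet) and 4.9.2.1, replace the option with the text below, and amend the formula and ESTIMATE line in 4.9.2.3 and 4.9.2 to match:

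*The 12-level nominal-time factor is kept in the primary model whatever Day -1 shows. The prediction at Cmax is averaged equally over the 12 nominal times. A (co)sine time function may be fitted as a sensitivity analysis only, with its prediction averaged over the same 12 times, and does not replace the primary 90% CI.*

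The cost is a few sentences and, if used, one extra sensitivity fit. No data are lost, and the SE of the time-averaged prediction is unchanged. The one downside is that clock-time variation between participants stays unmodelled in the primary analysis; the sensitivity fit is the place to look at it.

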**Linear relationship between paroxetine relationship and  $\Delta$ QTcF**

The linear relationship will be assessed using a scatter plot of  $\Delta$ QTcF (y-axis) vs. concentrations (x-axis), with linear and non-linear (loess) trend lines. The trend lines, directly obtained from the SAS® graphical procedures, will not reflect the model fit of the data but rather rough fixed regressions (without random effects) to detect drug effect and whether there are major violations to the linear assumption (in case of drug effect)

In case of the linearity assumption cannot be accepted, alternative models will be explored. A non-linear alternative could be, for example, the Emax model for which the linear component  $((\theta_1 + \eta_{1,i}) * C_{i,k})$  is replaced by a component of the form  $(\theta_{1,1} + \eta_{1,i}) * C_{ik}^\gamma / (\theta_{1,2}^\gamma + C_{ik}^\gamma)$ , where  $\theta_{1,1}$  is the maximal asymptotic increase from  $\theta_0$ ,  $\theta_{1,2}$  is the concentration at which the effect is half  $\theta_{1,1}$ ,  $\gamma$  is the hill coefficient and  $\eta_{1,i}$  is the random effect associated with  $\theta_{1,1}$ .

As such an example for a full nonlinear model could be written as :

$$\Delta QTc_{i,k} = (\theta_0 + \eta_{0,i}) + (\theta_{1,1} + \eta_{1,i}) * \frac{C_{ik}^\gamma}{\theta_{1,2}^\gamma + C_{ik}^\gamma} + \theta_{2,k} * TIME_{i,k} + \theta_3 (QTc_{i,k=0} - \overline{QTc_0}) + \varepsilon_{i,k}$$

The model parameters will be estimated including the precision around the parameter estimates using a maximum likelihood approach. Initial values will be determined from the graphical display.

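### SAP 4.9.2 fits the deciding linear model by maximum likelihood, so the standard error behind the 10 msec rule is about 2-3% too small; REML would correct it

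*SAP*

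**What the plan says.** SAP 4.9.2 specifies a linear mixed model for ΔQTc. The fixed effects are centred baseline, categorical time and concentration; the random effects are a participant intercept and slope with unstructured covariance. On estimation the text says: "The model parameters will be estimated including the precision around the parameter estimates using a maximum likelihood approach". The printed PROC MIXED call agrees: "NOITPRINT CL NOCLPRINT METHOD=ML PLOTS=NONE". The MODEL statement adds Kenward-Roger degrees of freedom: "MODEL CHG=BASEC ATPTN PCSTRESN / DDFM=KR SOLUTION ALPHAP=.05 CL RESIDUAL". REML is not mentioned.

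SAP 4.9.2.3 builds the two-sided 90% interval at the 60 mg geometric mean Cmax from the variances and covariance of the estimated intercept and slope. If the upper limit "falls below the 10 msec mark, the conclusion of the study is that there is no clinically relevant QTc prolongation" up to and including 60 mg.

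SAP 4.9.2 also allows simpler random-effect structures where the unstructured matrix "is not supported by the data or results in null estimates, and may result in non-convergence problems". It lists two variance components first, then "variance component with 1 random effect for intercept or slope".

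For the nonlinear alternative, SAP 4.9.2.1 repeats the estimation sentence: "using a maximum likelihood approach. Initial values will be determined from the graphical display". Protocol 9.3.2.2 names no estimation method and leaves the detail to the SAP.

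**The concern.** Maximum likelihood estimates variance components as if the fixed effects were known. With 36 to 40 participants, and fixed effects that use up participant-level information, the components come out too small on average, and so does the standard error of the predicted ΔQTc. Kenward-Roger adjusts for the uncertainty of the variance estimates. It does not correct the downward bias that maximum likelihood puts into them.

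The direction matters more than the size. The trial seeks to exclude an effect of 10 msec, so a standard error that is too small lowers the upper limit and makes a conclusion of no prolongation slightly too easy. No other planned analysis would offset this: the sensitivity analysis in SAP 4.9.5 concerns only how Cmax is obtained, and SAP 4.9.6 plans no supplementary analysis.

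**Working it through.** **The plan's own figures.** The documents give no standard error, variance or ML-versus-REML comparison. The nearest figure is the 82.5% probability that the upper limit is at least 10 msec when the true effect is 10 msec (N=36, no dropout; SAP 4.16). An unbiased estimate with a valid two-sided 90% interval gives Φ(1.645) = 95%, whatever the SD or N. The 82.5% is not reproduced, and the simulation inputs are not stated.

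**Inputs from the documents.** N is 36 to 40. There are 12 time points per visit. Day -1 values after baseline enter with concentration 0. A completer therefore contributes 11 + 3 × 12 = 47 records. The model has 14 fixed effects: intercept, baseline, concentration and 11 time contrasts.

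**Closed-form approximation.** Two participant-level fixed effects (intercept and baseline covariate) bear on the intercept variance, and one bears on the slope variance. The ML/REML ratio of standard errors then lies roughly between √((N−2)/N) and √((N−1)/N).
- N=36: √(34/36) = 0.972 to √(35/36) = 0.986, so ML is 1.4% to 2.8% too small.
- N=40: √(38/40) = 0.975 to √(39/40) = 0.987, so 1.3% to 2.5% too small.

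The one-sided error becomes Φ(−1.645 × ratio): Φ(−1.622) = 5.2% at 0.986 and Φ(−1.599) = 5.5% at 0.972.

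**Simulation, N=36, 4,000 trials per setting.** Assumed, not in the documents: geometric mean Cmax 20/50/90 for the three doses, log-SD 0.5, trough/peak ratio 0.6, residual SD 5 msec, between-participant SD 15 msec. The prediction is taken at the mean of the 12 time levels and the mean baseline. The time average is a choice of this check, since the formula in SAP 4.9.2.3 shows no time term. Both fits use Kenward-Roger. Coverage is the chance that the upper limit is at or above the true effect.

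| Slope SD at 60 mg Cmax (msec) | SE, ML | SE, REML | ML too small by | Coverage, ML | Coverage, REML |
|---|---|---|---|---|---|
| 0 | 0.797 | 0.821 | 2.9% | 94.8% | 95.5% |
| 1 | 0.823 | 0.846 | 2.7% | 94.4% | 95.0% |
| 2 | 0.885 | 0.908 | 2.5% | 94.3% | 94.9% |
| 3 | 0.978 | 1.002 | 2.4% | 94.6% | 95.2% |
| 4 | 1.087 | 1.111 | 2.2% | 94.9% | 95.2% |
| 6 | 1.347 | 1.374 | 2.0% | 94.8% | 95.2% |

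The Monte Carlo standard error is about 0.35 points per coverage figure. Six further settings varied dropout, residual SD and between-visit variance. Over all 12 settings the ML standard error is 1.9-2.9% below REML, the upper limit is 0.04-0.09 msec lower, and the one-sided error is 0.2-0.7 points higher. As a check on the first row: (0.821 − 0.797) × about 1.69 ≈ 0.04 msec.

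**Second simulation, different assumptions.** Residual SD 6 msec, random-intercept SD 3 or 6, slope SD 1.5, 4 or 8 at Cmax, concentration CV 60%, 200-300 replicates per setting. The ML/REML ratio is 0.973-0.981 at N=36, 0.975 with the SAP's dropout scenario and 0.979 at N=40. With Kenward-Roger on both fits it is 0.972-0.981. ML with Kenward-Roger is still 1.5-2.1% below plain REML. The upper limit moves by 0.03-0.06 msec. With 200 replicates the Monte Carlo standard error of an error rate is √(0.05 × 0.95/200) = 1.5 points, so this run supports the ratio but not an error rate.

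**Fallback structures.** Four readings of the not-supported trigger were tried: null slope estimate, AIC, BIC, and Wald p above 0.05. Coverage was 93.7-95.2%, against 94.2-95.3% for the full model. The largest loss was 0.7 points (93.7% against 94.4%, Wald rule, slope SD 1).

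**The case against.** The strongest reply is that the effect is negligible. The limit moves by less than 0.1 msec against a 10 msec margin, and ML coverage is close to 95%. The chance that ML and REML lead to different verdicts is at most about 0.4 × 0.041/0.82 = 2% (peak normal density times shift over standard error), and only if the true effect puts the limit near 10 msec. The plan is also unambiguous, since text and code agree. All of this stands, and it limits the weight of the point. It does not make the interval correct.

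A second reply is that ML may be intended for comparing fixed-effect forms, because the SAP allows a cosine time term or an Emax curve, and REML likelihoods are not comparable across different fixed effects. The SAP does not state that purpose. Even so, forms can be compared by ML and the chosen linear model refitted by REML for the interval.

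Two stronger readings are tempting. A reader might infer that the fallback wording leaves the analyst free to drop a real random slope and obtain a much too narrow interval. The documents do not support this. The structures are listed from richer to simpler, the first step keeps the slope, and two of the three triggers (null estimates and non-convergence) can be observed. Plausible readings of the third cost little. What remains is conditional: if a real slope were dropped, for example after a numerical failure, the model-based standard error would be too small. How often that would happen cannot be derived from the documents, and its size depends on the assumed slope SD. That the model-based formula would apply after reduction is also an inference, because code for the reduced models is not printed.

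A reader might also infer that ML explains the 82.5% in SAP 4.16. It does not. Since 82.5% corresponds to z = 0.935, and 0.935/1.645 = 0.57, it would need a standard error about 43% too small. ML accounts for 2-3%.

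**Conclusion.** The point holds as a minor one. The deciding linear fit uses maximum likelihood, and its standard error at N=36 is about 2-3% too small, with or without Kenward-Roger. The upper limit is about 0.04-0.09 msec too low, and the one-sided error at a true 10 msec is about 0.2-0.7 points above its nominal 5%. The ratio of standard errors is well supported: the closed form needs only N, and two simulations with different assumptions agree with it. The msec and error figures rest on assumed SDs and pharmacokinetics. The bias would rarely change the conclusion, but it runs in the anti-conservative direction and is simple to remove. The fallback order is a secondary matter of tidiness, not a demonstrated flaw.

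**What to change.** In the SAP 4.9.2 code, change METHOD=ML to METHOD=REML for the final linear model that supplies the 90% interval, and amend the estimation sentence there to match. State that ML may still be used to compare alternative fixed-effect forms, with the chosen linear model then refitted by REML. The corresponding sentence for the nonlinear alternative in SAP 4.9.2.1 can stay.

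Optionally, add one sentence to SAP 4.9.2 that makes the listed order binding:
1. If the failure is numerical, rescale concentration and CMAX60MG by the same factor and refit.
2. Then use two variance components.
3. Then use one random effect, dropping the slope only if its variance is estimated at zero or the two-component model still cannot be fitted.

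The cost is one code option and one or two sentences before database lock, recorded on the modification form that SAP Section 1 provides for. Protocol 9.3.2.2 need not change. The upper limit rises by less than 0.1 msec.
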